11.2.3. Demography

- Age: Age at the reference activity, computed as the number of units between the date of birth and the reference activity.

11.2.4. Immunogenicity

- For a given subject and given immunogenicity measurement, missing or non-evaluatable measurements will not be replaced.
- The Geometric Mean Concentrations/Titres (GMC/Ts) calculations are performed by taking the anti-log of the mean of the log titre transformations. Antibody titres below the cut-off of the assay will be given an arbitrary value of half the cut-off of the assay for the purpose of GMT calculation. The cut-off value is defined by the laboratory before the analysis and is described in Section 5.7.3 of the protocol.
- A seronegative subject is a subject whose antibody titre is below the cut-off value of the assay. A seropositive subject is a subject whose antibody titre is greater than or equal to the cut-off value of the assay.
- A seroprotected subject is a subject whose antibody concentration/titre is greater than or equal to the level defining clinical protection.
- The assay cut-off is the value under which there is no quantifiable result available. For an assay with a specific 'cut_off' , numerical immuno result is derived from a character field (rawres):
 - If rawres is 'NEG' or '-' or '(-)', numeric result= cutt_off/2,
 - if rawres is 'POS' or '+' or '(+)', numeric result = cut_off,
 - if rawres is '< value' and value<=cut_off, numeric result =cut_off/2,
 - if rawres is '< value' and value>cut_off, numeric result =value,
 - if rawres is '> value' and value<cut_off, numeric result =cut_off/2,
 - if rawres is '> value' and value>=cut_off, numeric result =value,
 - if rawres is '<= value' or '>= value' and value<cut_off, numeric result =cut_off/2,
 - if rawres is '<= value' or '>= value' and value>=cut_off, numeric result =value,
 - if rawres is a value < cut_off, numeric result = cut_off/2,
 - if rawres is a value >= cut_off, numeric result = rawres,
 - if rawres is a value >= cut_off, numeric result = rawres,
 - else numeric result is left blank.
- All CI computed will be two-sided 95% CI.

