6.3.2. Additional considerations

The following seropositivity thresholds are applicable:

- anti-RV IgA antibody concentration ≥ 20 U/mL.
- anti-diphtheria antibody concentrations \geq assay cut-off
- anti-tetanus antibody concentrations \geq assay cut-off
- anti-PT antibody concentrations ≥ 2.693 IU/mL
- anti-FHA antibody concentrations ≥ 2.046 IU/mL

The following seroprotection thresholds are applicable:

- anti-diphtheria antibody concentrations ≥ 0.1 IU/ml;
- anti-tetanus antibody concentrations ≥ 0.1 IU/ml;
- anti-poliovirus types 1, 2 and 3 antibody titres ≥ 8 .

Other cut-offs to be considered for summary tables and between-group comparisons

- Anti-PT antibody concentrations ≥ 10 IU/mL
- Anti-FHA antibody concentrations ≥ 10 IU/mL

Anti-rotavirus IgA antibody GMCs and their 95% CI will also be computed on subjects seropositive for anti-rotavirus IgA antibody.

A sensitivity analysis excluding forced randomization will be performed for the primary objectives in case the percentage of forced randomizations exceed 5% (forced randomizations are allocation which were constrained by supply available at the site. In open studies, allocations without using the randomization system are also forced randomizations).

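### Under the SAP's serology derivation rule, an anti-PT or anti-FHA report of `<10` IU/mL, if one occurs, becomes 10 and counts as meeting the primary ≥10 IU/mL endpoint (minor; the effect may be nil)

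*SAP*

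**What the plan says.** SAP 11.2.4 derives every numeric serology result from a character field. For a left-censored report with a bound above the assay cut-off the rule is: "if rawres is '< value' and value>cut_off, numeric result =value". A companion branch treats both directions of the inclusive form alike: "if rawres is '<= value' or '>= value' and value>=cut_off, numeric result =value". A left-censored report with a bound at or below the cut-off gets half the cut-off instead.

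The cut-offs for pertussis follow from two places. SAP 11.2.4 ties seropositivity to the assay cut-off ("A seropositive subject is a subject whose antibody titre is greater than or equal to the cut-off value of the assay"), and SAP 6.3.2 gives the seropositivity thresholds as "anti-PT antibody concentrations ≥ 2.693 IU/mL" and "anti-FHA antibody concentrations ≥ 2.046 IU/mL".

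The primary criterion for both antigens is an inclusive 10 IU/mL (SAP 3.1 and 4.1). SAP 6.3.2 repeats it under "Other cut-offs to be considered for summary tables and between-group comparisons". SAP 6.3.1 counts subjects at or above the cut-off and makes no exception for censored results.

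**The concern.** A laboratory report of `<10` states that the concentration is below 10. The derivation places it exactly on its bound, and an inclusive threshold at 10 then passes it. A known non-responder is scored as a responder on a primary non-inferiority endpoint. The neighbouring branch, for bounds at or below the cut-off, does put the result below the reported bound, so the two branches treat the same kind of information differently.

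At stake is the percentage above 10 IU/mL for anti-PT and anti-FHA, and through it the lower confidence limit compared with -10%. SAP section 7 makes the interpretation hierarchical, so a wrong verdict on one antigen would carry to whatever is tested after it. The figure with the order is not reproduced in the text at hand, so the position of PT and FHA is not claimed here.

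**Working it through.** **Step 1: apply the rule literally.** Inputs are the branches of SAP 11.2.4, the cut-offs 2.693 (PT) and 2.046 (FHA) from 6.3.2, and the ≥10 IU/mL criterion from 3.1 and 4.1.

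| Raw report | Derived, PT | Derived, FHA | Scored ≥10 | What the report supports |
|---|---|---|---|---|
| `<2.0` | 1.3465 | 1.023 | no | no |
| `<5` | 5 | 5 | no | no |
| `<9.9` | 9.9 | 9.9 | no | no |
| `<10` | 10 | 10 | **yes** | **no** |
| `<=10` | 10 | 10 | yes | open |
| `<20` | 20 | 20 | yes | open |
| `>5`, `>=5` | 5 | 5 | no | open |
| `POS` | 2.693 | 2.046 | no | open |

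Of these, only `<10` is scored against what the report says. The last four rows are unresolved, and the plan scores some as responders and others as non-responders.

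Anti-RV IgA is not affected at its own threshold: the cut-off is 20, so `<20` becomes 20/2 = 10, which is seronegative. For diphtheria, tetanus and polio the SAP gives no numeric assay cut-off, so the same check cannot be made.

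**Step 2: choose the interval.** The lower limit is the value d below the observed difference that solves (p1 − p2 − d)/√V(d) = 1.96. Here V(d) = [r1(1 − r1)/n1 + r2(1 − r2)/n2] × N/(N − 1), r1 and r2 are the maximum-likelihood rates under a difference of d, and N = n1 + n2. This is the Miettinen-Nurminen score interval, taken as the standardised asymptotic method named in SAP 11.1. Check against the plan's own figure: for 219/219 v 214/214 it gives -2.25 to 2.30 at 97.5% confidence, the limits printed in mock Template 15, whose footnote says 97.5%. At 95% it gives -1.73 to 1.77.

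**Step 3: one report.** The SAP gives no frequency of such reports, no expected response rates and no ATP cohort size. Assumed: 146, 131 or 117 per group (0%, about 10% and about 20% of 146 excluded), at least 80% responders in each arm, and a correct lower limit within 1.5 points of -10%. Change in the lower limit, in points, when one `<10` report is scored as a responder:

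| n per group | Co-administration only | Staggered only | One in each arm |
|---|---|---|---|
| 146 | +0.74 to +0.91 | -0.63 to -0.60 | +0.11 to +0.29 |
| 131 | +0.83 to +1.04 | -0.70 to -0.66 | +0.13 to +0.34 |
| 117 | +0.93 to +1.16 | -0.78 to -0.74 | +0.16 to +0.41 |

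A fail becomes a pass only if the correct limit is no lower than -10.71 (146), -10.94 (131) or -11.02 (117). A pass becomes a fail only if it is no higher than -9.39, -9.34 or -9.26.

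Examples at 131 per group, Co-administration v Staggered:
- 121 v 126 gives -10.17 (fail); derived as 122 v 126 it gives -9.23 (pass).
- 120 v 124 gives -9.77 (pass); derived as 120 v 125 it gives -10.43 (fail).
- 124 v 124 gives -5.99; derived as 125 v 125 it gives -5.67 (both pass).

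**Step 4: several reports, all in Co-administration (assumed).**

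| n per group | Derived counts, both arms | `<10` reports | Correct lower limit | Derived lower limit |
|---|---|---|---|---|
| 146 | 146 | 7 | -9.58 | -2.57 |
| 146 | 146 | 8 | -10.45 | -2.57 |
| 146 | 146 | 12 | -13.83 | -2.57 |
| 146 | 139 | 6 | -10.46 | -5.40 |
| 131 | 131 | 7 | -10.63 | -2.86 |
| 131 | 124 | 5 | -10.68 | -5.99 |

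So the restriction to results near the margin holds for one report, not for a cluster in one arm.

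**The case against.** The strongest objection is that the branch may never be reached for pertussis. SAP 11.2.4 says: "The assay cut-off is the value under which there is no quantifiable result available". With cut-offs between 2 and 3 IU/mL, a concentration between the cut-off and 10 would normally be reported as a number, and an ordinary left-censored report would be below the cut-off and handled correctly. The rule sits in an annex of standard derivations that covers many kinds of raw string for any assay. All of this stands, and it is why the point is minor. It does not make the rule right: that branch serves only reports censored above the cut-off, and at 10 it gives the wrong answer.

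It could also be called a convention for geometric means only. But the list is introduced as deriving the numeric result in general, and no separate derivation is given for threshold endpoints.

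A reader might infer that `<=10` and `<20` should simply be dropped, citing "missing or non-evaluatable measurements will not be replaced". The SAP does not support this. That sentence does not call censored reports non-evaluable, and the same section assigns them numbers. Dropping only these would also remove unresolved results now scored as responders while keeping `>5`, `>=5` and `POS` as non-responders.

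**Conclusion.** Wrong as written, and minor. If an anti-PT or anti-FHA report of `<10` occurs, the plan scores it as meeting an endpoint that it is known to miss.

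The effect may be nil. Under the assumptions of step 3, a single report changes the verdict only when the correct lower limit is between about -11.0% and -9.3%. Several in one arm could change it further out, as step 4 shows, but those counts are assumed.

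A reader might infer that the plan biases the pertussis comparison towards non-inferiority. The SAP does not support that: the rule applies to both arms, the direction depends on how any such reports split between them, and nothing shows that there are any. Nor can the defect be asserted for diphtheria, tetanus or polio. It would arise there only if the assay cut-off lay below the protection threshold, and the SAP does not give those cut-offs as numbers.

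**What to change.** Add to SAP 11.2.4 that, for threshold endpoints, a `< value` result never counts as reaching a threshold at or above that value, so `<10` is a non-responder for ≥10 IU/mL. Apply the same classification to the reverse cumulative curves, or footnote the difference. Leave the GMC/GMT calculation unchanged; such a subject would still enter the geometric mean at 10.

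Tabulate by group and antigen every censored or qualitative result whose bound does not settle the threshold, in both directions (`<=10`, `<20`, `>5`, `>=5` and `POS` against 10). If any occur, handle them symmetrically, for example by a sensitivity analysis that scores them each way.

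The cost is a few sentences of SAP text and a minor programming check. A few results may become non-responders. If no such reports exist, the table shows it and nothing else changes.

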11.2.5. Safety

- For analysis of solicited, unsolicited adverse events (such as serious adverse events or adverse events by primary MedDRA term) and for the analysis of concomitant medications, all vaccinated subjects will be considered. Subjects who did not report the event or the concomitant medication will be considered as subjects without the event or the concomitant medication respectively.

- In case there will be more than 5% of subjects without documented dose for solicited symptoms (i.e., symptom screen not completed), sensitivity analysis will include only vaccinated subjects for doses with documented safety data (i.e., symptom screen completed).
- The following rules will be used for the analysis of solicited symptoms:
 - Subject who didn't document the presence or absence of a solicited symptom after one dose will be considered not having that symptom after that dose in the analysis done on "administered dose"
 - Subjects who documented the absence of a solicited symptom after one dose will be considered not having that symptom after that dose.
 - Subjects who documented the presence of a solicited symptom and fully or partially recorded daily measurement over the solicited period will be included in the summaries at that dose and classified according to their maximum observed daily recording over the solicited period.
 - Subjects who documented the presence of a solicited symptom after one dose without having recorded any daily measurement will be considered as having that symptom after that dose).
- The maximum intensity of local injection site redness/swelling will be coded as follows:

| Grade | Redness/swelling |
|-------|-------------------------|
| 0 | Absent |
| 1 | > 0 mm and \leq 5 mm |
| 2 | > 5 mm and \leq 20 mm |
| 3 | > 20 mm |

- For the analysis, temperatures will be coded as follows for oral, axillary or tympanic route:

| Grade | Temperature |
|-------|-------------------------------|
| 0 | < 37.5°C |
| 1 | \geq 37.5°C - \leq 38.0°C |
| 2 | > 38.0°C - \leq 39.0°C |
| 3 | > 39.0°C |

For rectal route, temperatures will be converted to axillary setting by subtracting 0.5°

- Note that for all tables described in this section, the way the percentage of subjects will be derived will depend on the event analysed (see table below for details). As a result, the N value will differ from one table to another.

| Event | N used for deriving % per subject for Vaccination phase | N used for deriving % per dose for Vaccination phase |
|---------------------------|--|--|
| Concomitant vaccination | All subjects with study vaccine administered | All study visits with study vaccine administered |
| Solicited general symptom | Primary analysis: all subjects with study vaccine administered Sensitivity analysis: all subjects with at least one solicited general symptom documented as either present or absent (i.e., symptom screen completed) | Primary analysis: all study visits with study vaccine administered Sensitivity analysis: all study visits with study vaccine administered and with at least one solicited general symptom documented as either present or absent (i.e., symptom screen completed) |
| Solicited local symptom | Primary analysis: all subjects with study vaccine administered Sensitivity analysis: all subjects with at least one solicited local symptom documented as either present or absent (i.e., symptom screen completed) | Primary analysis: all study visits with study vaccine administered Sensitivity analysis: all study visits with study vaccine administered and with at least one solicited local symptom documented as either present or absent (i.e., symptom screen completed) |
| Unsolicited symptom | All subjects with study vaccine administered | All study visits with study vaccine administered |
| Concomitant medication | All subjects with study vaccine administered | All study visits with study vaccine administered |

- All CI computed will be two-sided 95% CI.

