6.4. Analysis of safety

6.4.1. Analysis of safety planned in the protocol

The safety analysis will be based on the TVC.

The incidence by dose, overall per dose and overall per subject, with its exact 95% CI of

- any adverse event (solicited or unsolicited, local or general),
- at least one local adverse event (solicited or unsolicited), and,
- at least one general adverse event (solicited or unsolicited),

during the 8-day (Days 0-7) follow-up period will be tabulated. The same calculations will be performed for any Grade 3 (solicited or unsolicited) symptoms, related and for any adverse event requiring medical attention.

For each type of solicited symptom, the incidence during the 8-day (Days 0-7) follow-up period of the symptom (any grade, Grade 3, related, Grade 3 related, requiring medical advice) will be tabulated as follows:

- at each dose, the percentage of doses followed by the reporting of a symptom and its exact 95% CI,
- over all the doses, the percentage of subjects reporting the symptom and its exact 95% CI,
- over all the doses, the percentage of doses followed by the reporting of a symptom and its exact 95% CI,
- for fever, additional analyses will be performed by 0.5°C increments.

The percentage of subjects who receive concomitant medication, who receive antipyretic medication and prophylactic antipyretic medication during the 8-day (Days 0-7) and 31-day (Days 0-30) follow-up period post-vaccination will be tabulated by dose, overall per subject and over all the doses.

The verbatim reports of unsolicited symptoms will be reviewed by a physician and the signs and symptoms will be coded according to MedDRA. Every verbatim term will be matched with the appropriate Preferred Term. The percentage of subjects with unsolicited symptoms occurring during the 31 days (Days 0-30) with its exact 95% CI will be

tabulated by preferred term. Similar tabulation will be done for Grade 3 unsolicited symptoms and for unsolicited symptoms causally related to vaccination.

Subjects who experienced at least one SAE during the entire study period (from the first dose till the end of the study [Visit 7]) will be reported and the SAEs will be described in detail.

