6.4.2. Additional considerations

- In line with the endpoint description separate analysis will be made for solicited symptom, unsolicited AE within 31 days post vaccination and concomitant medication for
 - The 2 HRV doses
 - The first DTPa-IPV dose
- In line with the HRV project standard, the primary analysis of solicited symptom will be performed by administered dose regardless of whether a solicited symptom has been documented as present/absent. A complementary analysis by documented dose in which only dose for which presence/absence of the symptoms is recorded will be performed in case the percentage of documented dose among administered dose exceed 5% for one visit or a group.
- The incidence by dose, overall per dose and overall per subject of any grade 3 adverse event (solicited or unsolicited, local or general) with causal relationship to vaccination during the 8-day (Days 0-7) follow-up period will be tabulated with exact 95% CI.
- The percentage of subjects with unsolicited symptoms requiring medical attention occurring within 31 days (Days 0-30) post-vaccination with its exact 95% CI will be tabulated by group and preferred term. Similar tabulation will also be done for unsolicited AEs rated as grade 3 in intensity with causal relationship to vaccination.
- The percentage of subjects with causally related AEs from the first study vaccine until Visit 7 will be tabulated by group and preferred term.
- Medications will be coded using the GSKDRUG dictionary. Medications which started during the specified periods (Days 0-7 and Days 0-30) will be counted rather than all medications taken during the specified periods.
- For clinicaltrials.gov and EudraCT posting purposes, a summary of subjects with all combined solicited (regardless of their duration) and unsolicited adverse events will be provided. Solicited adverse events will be coded by MedDRA as per the following codes:

| Solicited symptom | Lower level code | Lower level term |
|----------------------------|------------------|---------------------------|
| Pain at injection site | 10022086 | Injection site pain |
| Redness at injection site | 10022098 | Injection site redness |
| Swelling at injection site | 10053425 | Injection site swelling |
| Fever | 10016558 | Fever |
| Irritability/Fussiness | 10057224 | Irritability postvaccinal |

| Solicited symptom | Lower level code | Lower level term |
|-------------------|------------------|------------------|
| Diarrhoea | 10012727 | Diarrhea |

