| | >40.0 | | | | | | | | | |
| | Related | | | | | | | | | |
| | >38.0 Related | | | | | | | | | |
| | >38.5 Related | | | | | | | | | |
| | >39.0 Related | | | | | | | | | |
| | >39.5 Related | | | | | | | | | |
| | >40.0 Related | | | | | | | | | |
| | Medical advice | | | | | | | | | |
| Overall/subject | | | | | | | | | | |
| Each symptom except fever | All | | | | | | | | | |
| | Grade 3 | | | | | | | | | |
| | Related | | | | | | | | | |
| | Grade 3 Related | | | | | | | | | |
| | Medical advice | | | | | | | | | |
| Fever/(Axillary) (°C) | All | | | | | | | | | |
| | ≥37.5 | | | | | | | | | |
| | >38.0 | | | | | | | | | |
| | >38.5 | | | | | | | | | |
| | >39.0 | | | | | | | | | |
| | >39.5 | | | | | | | | | |
| | >40.0 | | | | | | | | | |
| | Related | | | | | | | | | |
| | >38.0 Related | | | | | | | | | |
| | >38.5 Related | | | | | | | | | |
| | >39.0 Related | | | | | | | | | |
| | >39.5 Related | | | | | | | | | |
| | >40.0 Related | | | | | | | | | |
| | Medical advice | | | | | | | | | |

HPV_2D = females aged 4-6 years who received two doses of HPV-16/18 L1 VLP AS04 vaccine at Day 0 and Month 6

MMR_DTPa = females aged 4-6 years who received MMR vaccine at Day 0 and DTPa vaccine at Month 6

For each dose and overall/subject:

N = number of subjects with at least one documented dose

n/% = number/percentage of subjects reporting the symptom at least once

For Overall/dose:

N = number of documented doses

n/% = number/percentage of doses followed by at least one type of symptom

95%CI = Exact 95% confidence interval; LL = lower limit, UL = upper limit

Template 24 Percentage of subjects reporting the occurrence of unsolicited symptoms classified by MedDRA Primary System Organ Class within the 31-day (Days 0-30) post-vaccination period (Total vaccinated cohort)

| Primary System Organ Class (CODE) | Preferred Term (CODE) | HPV_2D | | | MMR_DTPa | | |
|---|---------------------------------|--------|---|--------|----------|---|--------|
| | | N | % | 95% CI | N | % | 95% CI |
| At least one symptom | | | | | | | |
| Blood and lymphatic system disorders (10005329) | Anaemia (10002034) | | | | | | |
| Ear and labyrinth disorders (10013993) | Ear pain (10014020) | | | | | | |
| Gastrointestinal disorders (10017947) | Abdominal pain (10000081) | | | | | | |
| | Abdominal pain upper (10000087) | | | | | | |
| | Anal fissure (10002153) | | | | | | |

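### The documented-dose sensitivity analysis keeps infants with only one of two HRV diaries in its overall-per-subject rate, so that row retains part of the bias it is meant to test

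*SAP*

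**What the plan says.** The primary analysis of solicited symptoms counts every administered dose and treats an undocumented symptom as absent. SAP 11.2.5 attaches that rule to the administered-dose analysis only.

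The check on it is described in two places as resting on documented doses alone. In 6.4.2 it is an analysis in which "only dose for which presence/absence of the symptoms is recorded will be performed". In 11.2.5, "sensitivity analysis will include only vaccinated subjects for doses with documented safety data".

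The denominators come from the table at the end of 11.2.5. For general symptoms, per subject, the entry reads "Sensitivity analysis: all subjects with at least one solicited general symptom documented as either present or absent (i.e., symptom screen completed"). Per dose, the check uses "all study visits with study vaccine administered and with at least one solicited general symptom documented as either present or absent".

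Template 23 in Annex 3, the mock table for this analysis, follows the same line. Its footnote for the by-dose and overall-per-subject blocks reads "N = number of subjects with at least one documented dose", with the numerator "n/% = number/percentage of subjects reporting the symptom at least once".

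The per-subject measure in 6.4.1 is "over all the doses, the percentage of subjects reporting the symptom and its exact 95% CI". Under 6.4.2 the two HRV doses are analysed as one set and the first DPT-IPV dose as another. General symptoms are solicited after each HRV dose and the first DPT-IPV dose, local symptoms after the first DPT-IPV dose only (section 2).

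**The concern.** An infant with HRV dose 1 documented and HRV dose 2 undocumented meets the at-least-one condition and enters the per-subject denominator. The numerator asks only whether the symptom was ever reported, so the missing diary cannot add a case. This follows from the two definitions together, whatever the SAP says elsewhere about blanks. For such infants the row brings back the assumption that 6.4.2 and 11.2.5 set out to remove.

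The analysis runs only when documentation is incomplete, which is when this matters. If the overall-per-subject rate hardly moves between the two analyses, a reader of that row may conclude that missing diaries are harmless, although the row could not have moved much.

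A second, smaller matter is the partly answered diary. The table treats one documented symptom and a completed symptom screen as the same condition, and they are not.

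**Working it through.** The SAP gives no expected symptom rate and no expected diary return, so there is no planned figure to reproduce. The inputs below are assumptions, except the two HRV doses and the 146 infants per group (SAP section 2).

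**Notation.** p = per-dose symptom rate; u = share of doses undocumented; b = share of infants with both HRV diaries missing. Missingness is taken as unrelated to symptoms and, for the worked cases, symptoms as independent between doses.

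- Exactly one diary missing: 2(u − b). None missing: 1 − b − 2(u − b).
- True per-subject rate: T = 1 − (1 − p)².
- Primary (administered-dose) rate: A = [1 − b − 2(u − b)]·T + 2(u − b)·p.
- Sensitivity rate as defined: D = A/(1 − b), because only infants with no diary leave N.
- Share of bias kept: (T − D)/(T − A).

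**Case 1: u = 0.10, p = 0.40, independent missingness.** b = 0.01, one missing 0.18, none missing 0.81. T = 1 − 0.36 = 64.0%. A = 0.81 × 0.64 + 0.18 × 0.40 = 59.0%. D = 0.5904/0.99 = 59.6%. Kept: 4.36/4.96 = 88%.

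**Case 2: same u and p, half of the undocumented doses in infants missing both diaries.** b = 0.05, one missing 0.10, none missing 0.85. A = 0.85 × 0.64 + 0.10 × 0.40 = 58.4%. D = 0.584/0.95 = 61.5%. Kept: 2.53/5.60 = 45%.

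**Case 3: same u and p, missing diaries always paired.** b = 0.10. A = 0.90 × 0.64 = 57.6%. D = 0.576/0.90 = 64.0%. Kept: none.

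**Case 4: u = 0.06, p = 0.20, independent missingness.** b = 0.0036. T = 36.0%, A = 34.1%, D = 34.2%.

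**Range.** Write b = u² + r·u(1 − u), with r the correlation of missingness between the two doses. Over p = 0.1 to 0.5, u = 5% to 20% and within-infant symptom correlation 0 to 0.3:

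| r | Share of bias kept |
|---|---|
| 0 | 70-95% |
| 0.5 | 29-47% |
| 1 | 0% |

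If no infant lacks both diaries, b = 0 and D = A, so the row cannot move. For example, with p = 0.30 and 10% of infants missing one diary, both analyses give 0.90 × 51.0% + 0.10 × 30% = 48.9%, against a true 51.0%.

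**Per-dose rates.** Visits without a diary leave the per-dose denominator. At p = 0.30 and u = 0.10 the administered-dose rate is 0.30 × 0.90 = 27% and the documented-dose rate 30%, so the bias is fully removed.

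**Partly answered diary.** If one documented symptom admits the visit for every symptom, 5% item non-response at p = 0.30 gives 0.30 × 0.95 = 28.5% per dose instead of 30%. That holds only under the literal wording of the table.

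**The case against.** Five points can be made against this.

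- **Other blocks work.** Template 23 has Dose 1, Dose 2, overall-per-dose and overall-per-subject blocks. Whole-diary bias leaves the first three when missingness is unrelated to symptoms, and Template 18 reports diary return by dose. A reader might infer that the whole check is uninformative. The SAP does not support that, because only the overall-per-subject row is affected.
- **Size rests on clustering.** Keeping most of the bias requires diaries to go missing independently within a family. If the same families return neither diary, little or none is kept. This stands, and only a range can be given.
- **Trigger.** Section 11.2.5 starts the check at more than 5% of subjects without a documented dose. If that means infants with no diary at all, Cases 1 and 4 (1% and 0.4%) and Case 2 (exactly 5%) would not trigger it. Just above the threshold, with u = 10%, b = 5.5% and p = 0.40, A = 0.855 × 0.64 + 0.09 × 0.40 = 58.3% and D = 0.5832/0.945 = 61.7%, so about 60% of the bias is removed. Section 6.4.2 words its trigger by dose, and on that reading all the cases could run.
- **Partly answered diary.** A reader might infer that the SAP scores a blank symptom as absent in this analysis. It states no such rule: missing-equals-absent is confined to the administered-dose analysis, and the reference to a completed screen suggests something stricter. This is an unclear definition, not a settled error.
- **The alternative loses known cases.** An infant with the symptom recorded after dose 1 and no second diary would be dropped. That is true, but selection is then on documentation, not outcome. Keeping such cases while dropping incomplete infants without the symptom would bias the rate upward.

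**Conclusion.** The point holds for one row: the HRV overall-per-subject rate of solicited general symptoms in the documented-dose analysis. That row keeps part of the downward bias whenever some infants have one of two HRV diaries. The part kept runs from most of it (independent missingness) to none (always paired), and the SAP gives nothing to place the trial within that range. At 10% undocumented and a 40% per-dose rate, the shortfall left after the check is 4.4 points under independence (64.0 − 59.6) and 2.5 points in Case 2 (64.0 − 61.5). These figures assume that missingness is unrelated to symptoms.

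Local symptoms and DPT-IPV dose 1 involve a single dose, so the two-diary problem cannot arise there. The results are descriptive and the table is conditional, and the non-inferiority objective is untouched. This is a cheap improvement, not a flaw in the trial's main conclusion.

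**What to change.** - In the 11.2.5 table and Template 23, for the HRV overall-per-subject sensitivity row, use N = infants with that symptom documented as present or absent after every HRV dose they received. Alternatively, add this as a second row beside the existing one.
- Reconcile the at-least-one-symptom condition with the completed-screen condition and with 6.4.2. Define the documented-dose denominator symptom by symptom, so that an unanswered symptom is not counted as absent.

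The cost is SAP wording and one denominator in the programs; no new data are needed. The new N loses infants with one missing diary. At 6% undocumented doses that is 146 × 2(0.06 − 0.0036) = 16.5 per group under independence, or 146 × 2(0.06 − 0.03) = 8.8 if half of the undocumented doses are in infants missing both, so about 9 to 17 of 146, with a slightly wider interval. The new row is unbiased only if missingness is unrelated to symptoms, and its footnote should say so.
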